## **5. TREATMENT OF SUBJECTS**

### **5.1 Investigational product/treatment**

KP (total- or unicompartmental KP, at the discretion of the treating orthopaedic surgeon in consultation with the patient) is performed according to NOV guidelines as used in clinical practice.

KJD is performed according to the NOV recommendations for clinical care (see appendix S).

### **5.2 Use of co-intervention (if applicable)**

Not applicable

### **5.3 Escape medication (if applicable)**

Not applicable. Patients may use (pain) medication (which will be recorded) according to regular care NOV and participating institute guidelines/recommendations. If needed further surgical interventions (e.g. arthroplasty or revision for KJD and KP) in line with regular care, NOV and local guidelines will be performed (and registered).

## **6. INVESTIGATIONAL PRODUCT**

Not applicable. As confirmed by the CCMO (email d.d. sept 8th 2021), this study does not fall within the scope of the medical device regulation.

**6.1 Name and description of investigational product(s)**

**6.2 Summary of findings from non-clinical studies**

**6.3 Summary of findings from clinical studies**

**6.4 Summary of known and potential risks and benefits**

**6.5 Description and justification of route of administration and dosage**

**6.6 Dosages, dosage modifications and method of administration**

**6.7 Preparation and labelling of Investigational Medicinal Product**

**6.8 Drug accountability**

## **7. NON-INVESTIGATIONAL PRODUCT**

Not applicable

**7.1 Name and description of non-investigational product(s)**

**7.2 Summary of findings from non-clinical studies**

**7.3 Summary of findings from clinical studies**

**7.4 Summary of known and potential risks and benefits**

**7.5 Description and justification of route of administration and dosage**

**7.6 Dosages, dosage modifications and method of administration**

**7.7 Preparation and labelling of Non Investigational Medicinal Product**

**7.8 Drug accountability**

## 8. METHODS

### 8.1 Study parameters/endpoints

#### 8.1.1 Main study parameter/endpoint

The primary outcome of this randomized non-inferiority trial is the WOMAC total score at 2 years. The Western Ontario and McMaster Universities Arthritis Index (WOMAC) total score (0-100; higher is better) is a combination of (sub scores for) pain, disabilities, and stiffness, all relevant to the patient, making it the preferred primary outcome for our study.

The WOMAC score is calculated based on the KOOS questionnaire (Appendix A), which is a freely available questionnaire (unlike the WOMAC questionnaire) and contains the same questions as the WOMAC and questions for two additional domains function in daily living and function in sports and recreation. Therefore, WOMAC scores are often calculated based on this instrument. Contrary to the KOOS scores, a total score (based on the individual sub-scores) can be calculated for the WOMAC, which is not advised for the KOOS (see [www.koos.nu](http://www.koos.nu)).

Finally, the WOMAC total score is one of the 'crucial endpoints' as defined in the StWP process by ZiN to decide on reimbursement for this promising treatment in consultation with all stakeholders (such as the professional and patient associations).

#### 8.1.2 Secondary study parameters/endpoints (if applicable)

- WOMAC sub-scores for pain, stiffness, and function (0-100)
- KOOS scores for Pain, Symptoms, Function in daily living (ADL), Function in sport and recreation (Sport/Rec), and knee related Quality of life (QOL) (all scored on a 0-100 scale)
- SF36 physical component score and mental component score (0-100)
- NRS-pain (0-10)
- Patient Acceptable Symptom State
- NRS-satisfaction (0-10)
- EQ5D-5L for generic Quality of Life
- Pain medication (custom made questionnaire to assess the use of pain medication during the assessment period (last week) of the KOOS pain questionnaire)
- (serious) adverse events; including pin-tract infections based on a custom made CRF.
- Occurrence of surgical reinterventions (KP and revision arthroplasty procedures)
- Radiographic Joint space width (for KJD only) in millimetres using KIDA (Knee Images Digital Analysis; 15) as well as overall K-L grade from the same image.

See Appendix A – N

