**Nature and extent of the burden and risks associated with participation, benefit and group relatedness:** The benefit of a KP over KJD might be the swifter and slightly better clinical effect of treatment although at the expense of the original joint and with the higher risk of revision surgery later in life. The benefit of the KJD over a KP is that the original joint is preserved with the chance of postponing placement of a KP and decreasing the chance of revision surgery later in life, although with the burden of a 6-week distraction period with the chance of skin pin-tract infections, and possibly a slightly (non-clinically relevant) lesser clinical benefit.

In both arms, at 7 moments questionnaires must be filled out without the need of a clinic visit. At baseline for both treatments, and in case of KJD treatment additionally at 24 months a clinic visit takes place (the latter for a study specific x-ray) in addition to the typically 4 clinic visits performed in regular practice. In both arms a comparable number of knee radiographs is made in regular care and for KJD the 24 months study specific x-ray will be made.

In both arms the chance of failure is <5% in the first year after treatment. Failure can be due to multiple reasons, mostly persisting pain, leading to either revision surgery in case of a KP or placement of a first KP in case of KJD. Additionally, there is a chance of infection in both arms. In case of KJD these are primarily superficial skin pin tract infections, in generally successfully treatable with oral antibiotics. In both arms a small chance for deeper infections up to osteomyelitis are seen, needing i.v. antibiotics and/or nettoyage or even removal of the frame in case of KJD or early revision surgery in case of KP. Rehabilitation after the intervention(period) is similar for both treatment arms.

Patients randomised to knee distraction in the GODIVA trial are asked to participate in this GODIVA-bone add-on study. In case of consent, the burden will be a knee-MRI, knee-CT, and DEXA scan at pre-treatment and 2 years post-treatment, which will take two times an 60-120 min extra out-patient visit time. These image techniques are considered minimally

[figure not shown]
invasive with CT and DEXA with radiation exposure. Additionally, a vena puncture for 2 times 7 cc blood samples (serum and plasma) at both timepoints provides a minimal risk. The urine samples are considered riskless. There is no direct benefit for the patient.

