### Secondary Objective(s):

- To determine whether KJD is non-inferior to usual care (KP) on patient reported effectiveness regarding secondary patient reported outcomes (e.g. WOMAC subscores for pain, disabilities and stiffness, quality of life) over 2 years.
- For KJD only: To determine the change in radiographic joint space width over 2 years compared to baseline (i.e. before KJD treatment) as a surrogate marker for cartilage tissue repair.
- To describe and compare adverse events between KJD and KP (including reoperations) over 2 years.
- In the **GODIVA-bone substudy**: to predict the beneficial effects of knee distraction treatment for patients with knee osteoarthritis, based on peri-articular bone characteristics.
- In the **GODIVA-bone substudy**: to elucidate the relationship between periarticular bone changes (pre- and 2 years post-treatment) and improvement in pain perception and cartilage repair.

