5. The clinical checks after surgery will be performed in line with local clinical practice. According to regular practice, patients treated with Knee prosthesis will visit the orthopaedic surgeon at ~6 and ~12 months after surgery for a clinical check. Patients treated with Knee Joint Distraction will visit the orthopaedic surgeon after ~3 weeks for a clinical check, at 6 weeks for removal of the distraction frame, and at ~6 months and at ~12 months after surgery for a clinical check. Although the clinic visits for check-up are not part of the study visits and follow regular care practice at the local center (and thus are not specifically depicted in above scheme), data on adverse events occurring will be specifically collected during the regular care visits in a standardized way (continuous registration, via standard notation in electronic health records and entered in Castor via EHR review). This is also the case for the standard measurement of knee flexion. Questionnaires will be sent to all participants via email (via Castor EDC) at 3 weeks and at 2, 5, 8, 12 and 24 months after surgery/start distraction period). At 12 and 24 months after surgery, only patients treated with joint distraction will be invited to come to the hospital for a radiograph of the knee (after 12 months is part of regular care according to NOV recommendations). At 24 months all patients will be contacted and asked if any additional surgical procedures of the knee have been performed or planned, which will be noted.

6. In case of early study termination, a phone call will be made to ask for the reason of termination and ask if any additional surgical procedures of the knee have been performed or planned.

**For the GODIVA-bone substudy:** Standard(ised) knee-MRI (single clinical time slot comprising 3 sequences), standard(ised) knee-CT, standard(ised) DEXA (according to the Imaging manual of the substudy), vena puncture for 2 times 7 cc blood and a urine sample will be collected at baseline and 2 years after treatment. Imaging and sampling will be performed as much as possible during the visits of the GODIVA study. Only for a limited number of patients extra visits may be needed.

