## **10.2 Secondary study parameter(s)**

The analysis for continuous secondary outcomes follow the analysis strategy of the primary outcome. Binary, secondary outcomes will be compared using logistic multi-level regression analysis. The stratification factors for randomization (center and gender) will be used as (fixed) covariates in the analysis and the analysis will be adjusted by a limited number of a priori defined prognostic factors (e.g. baseline WOMAC total score, age, BMI, and severity of joint damage). Relative Risks (RR) with 95% confidence intervals will be estimated.

The upper limit (lower limit for response outcomes) of the confidence interval will be compared to the respective pre-defined non-inferiority limits to determine 'non-inferiority'. An ITT and a PP analysis will be performed.

The number of complications will be reported as the frequency and percentage of events and frequency and percentage of patients experiencing events per (type of) complication. Additional arthroplasty procedures, specifically a primary knee prosthesis after KJD and revision surgery (e.g. total after hemi prosthesis) after a primary knee prosthesis will be described per group.

Radiographic assessment of joint space width, as an indicator of cartilage repair, over a two-year period will be reported descriptively in the KJD group. Differences from baseline (pre-treatment) will be tested with paired t-tests or Wilcoxon rank sum tests depending on the distribution of the data at 1 and 2 years follow-up.

Missing data will be minimised using centralised data acquisition for all participating centers coordinated from the UMC Utrecht with appropriate monitoring on data queries and will be imputed using multiple imputation by chained equations for the analyses.

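### The reintervention endpoint counts only arthroplasty: after deep infection a KP revision is an event and a KJD frame removal is not, which can tilt the reoperation comparison towards KJD

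*Protocol*

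**What the plan says.** - **Objective.** Protocol section 2, secondary objectives: "To describe and compare adverse events between KJD and KP (including reoperations) over 2 years". Reoperations are not restricted by type.
- **Endpoint.** Section 8.1.2: "Occurrence of surgical reinterventions (KP and revision arthroplasty procedures". Only two kinds of operation qualify. A separate bullet covers (serious) adverse events, including pin-tract infections.
- **Analysis.** Section 10.2 carries the same restriction: "Additional arthroplasty procedures, specifically a primary knee prosthesis after KJD and revision surgery (e.g. total after hemi prosthesis) after a primary knee prosthesis" are to be reported, with the sentence ending "after a primary knee prosthesis will be described per group". The same section has a general rule: "Binary, secondary outcomes will be compared using logistic multi-level regression analysis", with relative risks and 95% confidence intervals. Complications are tabulated by type, as events and as patients.
- **Deep infection.** Summary, repeated in 11.4: "In both arms a small chance for deeper infections up to osteomyelitis are seen", and these are described as "needing i.v. antibiotics and/or nettoyage or even removal of the frame in case of KJD or early revision surgery in case of KP".
- **Data capture.** Section 8.3 registers additional surgical procedures continuously through regular care. At 24 months every patient is "asked if any additional surgical procedures of the knee have been performed or planned, which will be noted".

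**The concern.** Reoperation is an important counterweight to a non-inferior WOMAC result, because failures in either arm can be rescued surgically. A reader of the trial report will take a line headed surgical reinterventions as the measure of that burden. If the line admits one arm's operation for a complication and leaves out the other arm's operation for the same complication, the between-arm contrast partly reflects the counting rule and not the treatments. The endpoint is also narrower than the objective it serves. No prespecified per-patient measure covers reoperations as such.

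**Working it through.** The protocol gives no figure for this endpoint, so there is none to reproduce. Its sample size concerns the WOMAC score only and does not enter here.

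**Step 1. Apply the 8.1.2 definition to the deep-infection account.**

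| Operation for deep infection | Arm | Event under 8.1.2? |
|---|---|---|
| Early revision | KP | Yes |
| Frame removal | KJD | No |
| Nettoyage | KJD, and KP if the sentence is read that way | No |

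The infection sentence can be read in two ways. Nettoyage may belong to KJD only, or to both arms with only the escalation differing by arm. The contrast between the first two rows survives either reading, because frame removal can occur only with KJD and prosthesis revision, as described there, only with KP.

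**Step 2. When does the counting rule favour KJD?** Let C be the counted and U the uncounted reoperations in each arm, with arms of equal size. The counted ratio is C_KJD / C_KP. The full ratio is (C_KJD + U_KJD) / (C_KP + U_KP). Cross-multiplying, the counted ratio lies below the full ratio exactly when

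U_KJD / C_KJD > U_KP / C_KP.

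The direction therefore depends on uncounted operations in both arms, not in KJD alone.

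**Step 3. Illustration.** From the protocol: 600 patients per arm (section 4.4) and failure below 5% in year 1 in both arms (Summary). Assumed, because the protocol is silent:
- b: arthroplasty for other reasons, 2% to 8% per arm
- q: reoperation for deep infection, 0.5% to 3% per arm
- s: share of KP infection operations that are nettoyage only, 0, one half or 1
- no KJD infection operation is counted, and each patient has at most one operation

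Formulas: KP counted = 600 × (b + q(1 − s)); KJD counted = 600 × b. The true ratio over all reoperations is (b + q)/(b + q) = 1.00 by construction.

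| s | KP at b = 5%, q = 1% | KJD | Counted ratio | Range over all b and q |
|---|---|---|---|---|
| 0 | 600 × 0.06 = 36 | 30 | 30/36 = 0.83 | 12/30 = 0.40 to 48/51 = 0.94 |
| 0.5 | 600 × 0.055 = 33 | 30 | 30/33 = 0.91 | 12/21 = 0.57 to 48/49.5 = 0.97 |
| 1 | 600 × 0.05 = 30 | 30 | 1.00 | 1.00 |

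**Step 4. Could it reverse?** Take the middle row. KJD has 30 counted and 600 × 1% = 6 uncounted, so U/C = 6/30 = 0.20. KP has 33 counted and 3 uncounted, so U/C = 3/33 = 0.09, and the tilt is towards KJD. It would reverse if KP had more than 0.20 × 33 = 6.6 uncounted reoperations of any kind. Nothing in the protocol excludes that.

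**The case against.** The strongest reply is that nothing is lost. All additional knee procedures are registered in both arms, infections fall under the adverse-event bullet, and 10.2 tabulates complications by type. This stands: the omitted operations remain visible, and it would be wrong to infer that they vanish from the trial. But operations spread over complication lines do not form a prespecified per-patient reoperation rate, which is what the objective calls for.

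Second, restricting the endpoint to arthroplasty matches the Summary's symmetric idea of failure: revision after KP, or a first KP after KJD. That is a coherent measure and a good reason to keep it as a subset. It does not make it a measure of reoperations.

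Third, several stronger readings are tempting and the protocol does not support them:
- *That the endpoint demonstrably biases the comparison towards KJD.* KP-arm nettoyage may be uncounted too, so the net direction is not established.
- *That the uncounted KJD operation is equivalent to a prosthesis revision.* The protocol lists them side by side for the same complication and does not equate them. Every KJD frame is in any case removed on schedule.
- *That the distortion can be put at 1.2 to 1.6.* Those ratios follow from adding an assumed 1% to 3% (6 to 18 patients) to KJD only, giving 36 to 48 against 30. They set the same quantity to zero for KP and treat the below-5% ceiling as a point value.
- *That leaving out procedures planned but not done at 24 months favours KJD.* A planned KP revision is left out in the same way.
- *That 10.2 rules out a comparison.* Its general rule for binary outcomes could supply one. The specific sentence on arthroplasty says only that procedures are described, so the two need reconciling.

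**Conclusion.** The point holds in a limited form. The endpoint is narrower than the objective, and within the protocol's own deep-infection account it treats the arms differently: KP revision counts, KJD frame removal does not. This can bias the reintervention comparison towards KJD. In the illustrated scenarios, which all assume equal true burden, the counted ratio was 0.40 to 1.00 against a true 1.00. The range shows only what assumed rates would do. The protocol speaks of a small chance of deep infection and gives no rate, and enough uncounted KP operations would remove or reverse the effect. The WOMAC endpoint, its analysis and the sample size are unaffected. The SAP is not at hand. The point rests on a counting rule and a reporting statement that the protocol itself fixes. It is a worthwhile correction at low cost, not a threat to the main conclusion.

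**What to change.** - **8.1.2:** add, as a secondary endpoint, any unplanned surgical procedure on the index knee after the allocated treatment. Include nettoyage and unplanned frame removal, exclude the scheduled frame removal, and apply the definition identically in both arms. Keep arthroplasty (KP after KJD, revision after KP) as a named subset.
- **10.2:** replace the descriptive-only statement with a between-arm estimate and 95% CI for both the wider endpoint and the subset, in line with the objective and the section's own rule for binary outcomes.
- **Optional:** list procedures planned but not yet performed at 24 months, descriptively, for both arms.

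The cost is wording in the protocol and SAP, since the procedures are already registered in both arms. The downside is that the reported reintervention rate, mainly for KJD, may look somewhat less favourable. No clinical management changes.

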### 8.1.3 Tertiary study parameters

- Medical Consumption Questionnaire (MCQ; Appendix Q) and Productivity Cost Questionnaire (PCQ; Appendix R)
- Knee flexion (using a goniometer as measured during regular clinical visits; Appendix O)

Primary, secondary and tertiary outcomes include all outcomes relevant to and often used in (knee-) OA studies. This list of outcomes is also fully in line with the Standard Set of outcome measures and case-mix factors for monitoring, comparing, and improving health care for patients with clinically diagnosed hip or knee osteoarthritis (OA), developed with a focus on defining the outcomes that matter most to patients (developed by ICHOM (16)).

### 8.1.4 Other study parameters (if applicable)

General demographics such as age, gender, BMI as well as clinical parameters such as previous surgery (Appendix P) at the index knee and current indication for type of KP (TKP or UKP) will be evaluated. Some of these are well known prognostic factors for the prognosis of knee OA and/or effectiveness of KP or KJD treatment (16) and as such may act as treatment effect modifiers which will be explored.

The (limited) preference patients (Appendix H) participating in the study may have for one of the treatments will be measured and the effect on treatment effectiveness explored. OA severity (measured by the Charnley score, Appendix I) and patients general health (ASA classification, Appendix J) will also be measured as a descriptive variable as well as to make future matching of patients to patients from the Dutch national registration of orthopaedic implants (LROI) possible (outside the scope of this proposal).

Finally, the Pain-Detect Questionnaire (Appendix K) will be assessed at baseline to identify neuropathic components of a patients' pain, which may also be relevant with regard to patients prognosis and treatment effects.

**For the GODIVA-bone substudy:** Evaluation of imaging markers will be performed in three stages.

In the first stage, bone parameters will be scored, as scoring would be easily feasible to apply in clinical practice for the assessment of suitability for KD treatment. From radiographs, subchondral bone structure, and osteophytes will be scored automatically, which can be done with KOALA software (ImageBiopsyLab; [Jansen M et al. Osteoarthr Imag 2022;100018]). From DEXA scans, the T- and Z-score output

will be used [Ishii Y et al. Open Orthop J 2016;10,]. From CTs, subchondral bone density, cysts and osteophytes will be scored using the OACT scoring system [Gielis W et al. J Pers Med 2020;11,]. From MRI scans, bone marrow lesions (BMLs) and cysts will be scored with the WOMBS scoring method [Roemer F et al. Osteoarthr Cartil 2016;24,].

**In the second stage of the GODIVA-bone substudy**, bone parameters will be measured as continuous parameters, which is more time consuming but results in more sensitive measures. From radiographs, subchondral bone density and osteophyte size will be measured using KIDA software [Marijnissen A et al. Osteoarthr Cartil 2008;16,; Jansen M et al. Osteoarthr Cartil 2021;29,]. Bone mineral density will be measured from DEXA scans [Lo G et al. Semin Arthritis Rheum 2018;48,]. Subchondral bone density, cortical bone thickness and osteophyte volume will be measured from CT scans [Mastbergen S et al. Osteoarthr Cartil 2022;30,]. BML and cyst volume will be measured from MRI scans [Roemer F et al. Osteoarthr Cartil 2010;18,].

**In the third stage of the GODIVA-bone substudy**, image classification machine learning models (like convolutional neural networks) will be used for all imaging types to classify (in our case predict) which patients will be clinical and/or structural responders. These models can be used restricted (i.e. the model can only look at bone) and unrestricted. Available baseline images will be divided in training, validation, and test sets, to develop and confirm results of machine learning algorithms. At present we have gained experience in this approach by ML using images of PsA patients [Arbabi S et al. 2022; ms in preparation]. Final algorithms can not only be used directly for prediction; looking at which parts of the images are most important for the ML model provides additional information on which (bone) sites and properties are important for clinical and/or structural response and thus allow the definition of new features or combined selection of features from imaging to use in an overall prediction model (see below).

For biochemical data we will use serum/plasma samples and urine samples. When all baseline samples are collected, the state-of-the-art selection of bone biomarkers at that time will be made, together with experts in the field (Nordic Bioscience), and analysed (within feasibility with respect to costs).

Where relevant these results will be integrated with the endpoint analyses of the GODIVA trial.

